6.4. Packaging and Labeling

The contents of the label will be in accordance with all applicable regulatory requirements.

6.5. Preparation/Handling/Storage/Accountability

Diphenhydramine, raxibacumab and AVA will be prepared, stored and administered according to current product label requirements [[Anthrax Vaccine Adsorbed Package Insert, 2012](#); [Raxibacumab Package Insert, 2012](#); [Diphenhydramine Package Insert](#)]. A description of the methods and materials required for preparation of raxibacumab and AVA will be detailed in a Study Specific Technical Agreement/Memo (TTS) or Pharmacy Manual which will be accompanied by a Quality Agreement.

When the individual dose of study treatments are prepared for a subject, the preparation of the dose will be confirmed by a second member of the study site staff.

Only subjects enrolled in the study may receive study treatment and only authorized site staff may supply or administer study treatment. All study treatments must be stored in a secure environmentally controlled and monitored (manual or automated) area in accordance with the labelled storage conditions with access limited to the investigator and authorized site staff.

The investigator, institution, or the head of the medical institution (where applicable) is responsible for study treatment accountability, reconciliation, and record maintenance (i.e. receipt, reconciliation and final disposition records).

Further guidance and information for final disposition of unused study treatment are provided in the Study Reference Manual (SRM).

Under normal conditions of handling and administration, study treatment is not expected to pose significant safety risks to site staff. Take adequate precautions to avoid direct eye or skin contact and the generation of aerosols or mists. In the case of unintentional occupational exposure notify the monitor, Medical Monitor and/or GSK study contact.

A Material Safety Data Sheet (MSDS)/equivalent document describing occupational hazards and recommended handling precautions either will be provided to the investigator, where this is required by local laws, or is available upon request from GSK.

6.6. Compliance with Study Treatment Administration

Subjects will receive raxibacumab intravenously in accordance with the approved dosing recommendations for adults [[Raxibacumab Package Insert, 2012](#)] and/or AVA subcutaneously in accordance with the approved dosing recommendations for adults [[Anthrax Vaccine Adsorbed Package Insert, 2012](#)]. Raxibacumab and AVA will be administered in opposite limbs. Each sequential AVA injection will be administered in a different injection site (e.g. alternating arms). Diphenhydramine, 25 to 50 mg, should be administered within 1 hour prior to raxibacumab infusion to reduce the risk of infusion reactions. Diphenhydramine route of administration (oral or IV) should be based on the

temporal proximity to the start of raxibacumab infusion. Administration will be recorded in the source documents and reported in the CRF.

Subjects will receive study treatment directly from the investigator or designee, under medical supervision. The date and time of each dose administered in the clinic will be recorded in the source documents. The dose of study treatment and study subject identification will be confirmed at the time of dosing by a member of the study site staff other than the person administering the study treatment.

Mild infusion site reactions have been observed in subjects dosed with raxibacumab, which have been successfully prevented using an anti-histamine prior to dosing.

Hypersensitivity reactions have been reported with AVA. Should symptoms of acute hypersensitivity occur, an extended period of monitoring may be appropriate, based on clinical judgement. Subjects should be made aware of the potential risk, the signs and symptoms of such reactions, and the importance of immediately seeking medical attention.

The schedule for the administration of study treatment is outlined in the Time and Events Tables (Section 7.1). The site staff should monitor any subject who may experience a hypersensitivity reaction following the administration of study treatment. Refer to Section 7.4.1 and [Appendix 4](#) for information on the procedures for recording and evaluating AEs/SAEs. The decision regarding the administration of the vaccine following a hypersensitivity reaction will be made by the investigator in consultation with the Medical Monitor based on the clinical evaluation of the subject.

6.7. Treatment of Study Treatment Overdose

For this study, any dose of study treatment greater than that described in the product label will be considered an overdose [[Anthrax Vaccine Adsorbed Package Insert, 2012](#); [Raxibacumab Package Insert, 2012](#); [Diphenhydramine Package Insert](#)].

GSK does not recommend specific treatment for a raxibacumab overdose

In the event of an overdose, the investigator should:

1. contact the Medical Monitor immediately
2. closely monitor the subject for AEs/serious adverse events (SAEs) and laboratory abnormalities until drug can no longer be detected
3. document the quantity of the excess dose as well as the duration of the overdosing in the CRF.

Since only AVA is dosed on more than one occasion, the decision regarding the administration of the second dose of vaccine will be made by the investigator in consultation with the Medical Monitor based on the clinical evaluation of the subject.

6.8. Treatment after the End of the Study

Subjects will not receive any additional treatment from GSK after completion of the study because only healthy volunteers are eligible for study participation.

6.9. Lifestyle and/or Dietary Restrictions

Subjects who have a history of regular alcohol consumption as defined in Section [5.2](#) will be excluded from the study.

During each dosing session, subjects will abstain from alcohol for 24 hours prior to the study visit.

6.10. Concomitant Medications and Non-Drug Therapies

6.10.1. Permitted Medications and Non-Drug Therapies

Concomitant medication may be considered on a case by case basis by the investigator in consultation with the Medical Monitor if required. Any concurrent medication administered to the subject during the study should be recorded in CRF. Tylenol, effective methods of contraception (detailed in [Appendix 3](#)), and the influenza vaccine will be permitted.

6.10.2. Prohibited Medications and Non-Drug Therapies

Subjects must abstain from taking prescription or non-prescription drugs (including vitamins and dietary or herbal supplements), within 7 days (or 14 days if the drug is a potential enzyme inducer) or 5 half-lives (whichever is longer) prior to the first dose of study medication until completion of the follow-up visit, unless in the opinion of the Investigator and sponsor the medication will not interfere with the study.

Medication prohibited during the course of this study include:

- immunoglobulins not included in this trial
- any blood products
- long-acting immune-modifying drugs (e.g. infliximab)
- chronic administration (defined as more than 14 consecutive days) of immunosuppressants or other immune-modifying drugs (such as corticosteroids). Inhaled, topical and intra-articular corticosteroids are allowed.
- administration of a vaccine not foreseen by the study protocol. This includes any type of vaccine such as (but not limited to) live, inactivated, and subunit vaccines. Influenza vaccine is permitted after Week 8.
- Administration of an investigational or non-investigational study vaccine/product (pharmaceutical product or device).

7. STUDY ASSESSMENTS AND PROCEDURES

Informed consent must be obtained prior to enrollment in the study and conduct of any study procedures.

Protocol waivers or exemptions are not allowed with the exception of immediate safety concerns. Therefore, adherence to the study design requirements, including those

specified in the Time and Events Tables (Section 7.1), are essential and required for study conduct.

This section lists the procedures and parameters of each planned study assessment. The exact timing of each assessment is listed in the Time and Events Table (Section 7.1). All data collected for this study will be recorded in the subjects' CRF.

The timing and number of planned study assessments, including safety assessments may be altered during the course of the study based on newly available data to ensure appropriate monitoring.

The change in timing or addition of time points for any planned study assessments must be documented in a Note to File which is approved by the relevant GSK study team member and then archived in the study sponsor and site study files, but this will not constitute a protocol amendment.

The IRB/IEC will be informed of any safety issues that require alteration of the safety monitoring scheme or amendment of the Informed Consent Form (ICF).

No more than 500 mL of blood will be collected over the duration of the study, including any extra assessments that may be required. The Time and Events Tables (Section 7.1) detail the timings for study assessment.

7.1. Time and Events Table

Table 1 Screening assessments for subjects administered AVA or co-administered raxibacumab and AVA

Screening Assessments	Days -36 to -15 ^a	Notes
Informed consent process	X	
Demographic information	X	
Inclusion/Exclusion criteria	X	
Medical history (includes substance usage and Family history of premature CV disease)	X	
Physical exam including height and weight	X	
Alcohol and Drug Screening	X	
Urinalysis	X	
Vital signs	X	
Hematology and clinical chemistry	X	Refer to Table 4 for specific laboratory tests.
HIV, Hep B and Hep C screen	X	
Review concomitant medications	X	
Serum or urine pregnancy test	X	
AE/SAE assessment	X	Will capture SAEs reported between Screening visit and Day -1.
Toxin Neutralizing Ab (TNA)	X	
Anti-PA Ab	X	

a. The screening window closes at Day -15 to allow all analyses to be completed to confirm subject eligibility.

Table 2 Treatment Group 1: Time and Events for subjects administered AVA

Protocol Activity	Study Visit						Notes
Assessments	Day -1 ^a	Day 1	Day 15 (± 2 days)	Day 29 (± 2 days)	Day 57 (± 2 days)	Day 183 (± 4 days)	
Inpatient visit	←X→						
Outpatient visit				←-----X-----→			
Urinalysis					X		
Admit to unit	X						
Randomization	X						
Discharge from unit		X					The subject will be discharged from the unit after all assessments are completed.
Vital signs	X	X		X	X	X	
Hematology and clinical chemistry	X			X	X		Refer to Table 4 for specific laboratory tests. On Day 29 the specimen will be collected prior to AVA injection.
Review concomitant medications	X		X	X	X	X	
Serum or urine pregnancy test	X		X	X	X	X	
AVA administration		X	X	X			Each sequential AVA injection will be administered in a different injection site (e.g. alternating arms).
AE/SAE assessment	X	X	X	X	X	X	
Toxin Neutralizing Ab (TNA)		X		X	X	X	On Days 1 and 29 the specimen will be collected prior to AVA injection.
Anti-PA Ab		X		X	X	X	On Days 1 and 29 the specimen will be collected prior to AVA injection.

a. Day -1 is the calendar day preceding Day 1; the designation "Day 0" is not used in this study.

Table 3 Treatment Group 2: Time and Events Table for subjects co-administered raxibacumab and AVA

Protocol Activity Assessments	Study Visit								Notes	
	Day -1 ^a	Day 1				Day 15 (± 2 days)	Day 29 (± 2 days)	Day 57 (± 2 days)	Day 183 (± 4 days)	
		pre-raxi infusion	0 hr	0.5 hr (± 5 min)	2-6 hrs					
Inpatient visit		X								
Outpatient visit						X				
Urinalysis										
Admit to unit	X									
Randomization	X									
Discharged from unit			X							The subject will be discharged from the unit after all assessments are completed.
Vital signs	X		X			X	X	X		
Hematology and clinical chemistry	X					X	X			Refer to Table 4 for specific laboratory test. On Day 29 the specimen will be collected prior to treatment administration.
Review concomitant medications	X				X	X	X	X		
Serum or urine pregnancy test	X				X	X	X	X		
Diphenhydramine administration		X								Diphenhydramine (25-50 mg) must be administered within 60 minutes prior to the raxibacumab infusion.
Raxibacumab administration			X							Raxibacumab infusion must be completely administered prior to first AVA dose on Day 1 and administered in opposite limb from AVA injection.
AVA administration			X			X	X			Each sequential AVA injection will be administered in a different injection site (eg. alternating arms).
AE/SAE assessment	X	X	X	X	X	X	X	X		
PK sampling		X	X	X	X	X	X	X	X	A blood specimen will be collected prior to raxibacumab infusion, 30 minutes post raxibacumab infusion (± 5 min), 2-6 hours post infusion on Day 1, and at Days 15, 29, and 57 (14, 28, and 56 days post raxibacumab administration). An additional sample will be collected at the Day 183 visit.
Anti-raxibacumab Ab		X					X	X		
Toxin Neutralizing Ab (TNA)		X					X	X	X	The Day 29 specimens will be collected prior to AVA administration.
Anti-PA Ab		X					X	X	X	The Day 29 specimens will be collected prior to AVA administration.

a. Day -1 is the calendar day preceding Day 1; the designation "Day 0" is not used in this study.

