3. OBJECTIVE(S) AND ENDPOINT(S)

[figure not shown]
Objectives	Endpoints
Primary	

 To compare the immunogenicity of AVA at 4 weeks after the first AVA dose, when AVA is administered alone or concomitantly with raxibacumab. 	
 Ratio of geometric mean concentrations (GMC) of anti-PA Ab at 4 weeks after the first AVA dose (prior to the third AVA dose), between the AVA alone and the AVA with raxibacumab treatment groups.
Secondary	

 To compare the immunogenicity of AVA at Weeks 8 and 26 after the first AVA dose, when AVA is administered alone 	
 Ratio of GMC of anti-PA Ab at Weeks 8 and 26 after the first AVA dose, between the AVA alone and the AVA with

Objectives	Endpoints
or concomitantly with raxibacumab.	raxibacumab treatment groups.

 To estimate and compare seroconversion, defined as a \geq 4-fold increase in toxin neutralizing activity (TNA) titer from baseline, at Weeks 4, 8 and 26 after the first AVA dose, when AVA is administered alone or concomitantly with raxibacumab. 	
 Percentage of subjects who seroconvert, at Weeks 4, 8 and 26 after the first AVA dose, between the AVA alone and the AVA with raxibacumab treatment groups.

 To describe the safety of AVA when co-administered with raxibacumab versus AVA alone. 	
 Rate of reported adverse events (AE) as well as review of vital signs, urinalysis and clinical laboratory data in the AVA alone and the AVA with raxibacumab treatment groups.

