7.2. Screening and Critical Baseline Assessments

After written informed consent is provided, the following data will be collected at the screening visit for all subjects:

- Demographic parameters: year of birth, gender, race, and ethnicity.
- Medical/medication/family history will be assessed as related to the inclusion/exclusion criteria listed in Section 5.
- Physical assessment data including vital signs (temperature, heart rate, systolic and diastolic blood pressure, respiratory rate), height and weight.
- Laboratory assessments (hematology, clinical chemistry)
- Urinalysis
- Alcohol, Drug, HIV, Hepatitis B and Hepatitis C screenings
- A serum or urine pregnancy test on women of childbearing potential
- Blood specimen for anti-PA Ab levels and TNA titers.
- Record of concomitant medications
- Monitoring and reporting of SAEs

The following will be collected as baseline data on Day -1:

- A serum or urine pregnancy test on women of childbearing potential
- Record of concomitant medications
- Vital signs
- Results from clinical chemistry and hematology laboratory evaluations (refer to [Table 4](#) for specific assessments)
- Monitoring and reporting of AEs including SAEs

The following will be collected as baseline data on Day 1 prior to study treatment administration:

- Blood specimen for anti-PA Ab levels and TNA titers

Additionally, for subjects randomized to Treatment Group 2, the following will be collected as baseline data on Day 1 prior to study treatment administration:

- Blood specimen for anti-raxibacumab Ab level

- Blood specimen for serum raxibacumab concentrations

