9.4.2.3. Safety Analyses

Clinical safety observations will include AEs, urinalysis, vital sign measurements, and clinical laboratory assessments. Safety data will be tabulated and, where appropriate, analyzed by the use of descriptive statistics. Safety data will be tabulated for the Safety Population.

The number (%) of subjects withdrawing from the study will be summarized for each treatment group and the number (%) subjects withdrawing for each individual reason will be summarized by treatment group.

Reported AEs will be coded using MedDRA. The number (%) of subjects in each treatment group with treatment-emergent AEs will be compared for overall incidence and by system organ class and preferred term. Similar summaries will also be presented for deaths, all SAEs, AEs leading to withdrawal, and drug-related AEs. Severity of treatment-emergent AEs will also be summarized by system organ class, preferred term, and treatment group.

Additionally, the frequency of laboratory abnormality events along with shifts from baseline will be summarized, as well as changes over time in laboratory parameters, urinalysis and vital signs.

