2.2.2 Secondary Endpoint(s)

- Ratio of GMC of anti-PA Ab at Weeks 8 and 26 after the first AVA dose, between the AVA alone and the AVA with raxibacumab treatment groups.
- Percentage of subjects who seroconvert, at Weeks 4, 8, and 26 after the first AVA dose, between the AVA alone and the AVA with raxibacumab treatment groups.
- Rates of reported adverse events (AE) as well as review of vital signs, urinalysis, and clinical laboratory data in the AVA alone and the AVA with raxibacumab treatment groups.

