2.6 Study Schedule

The study will be comprised of a screening period (Days -36 to -15) and a treatment period (Days -1 to 183 ± 4). The complete schedule of visits and all procedures is presented in Table 2. 1, Table 2. 2, and Table 2. 3

Table 2.1 Screening assessments for subjects administered AVA or co-administered raxibacumab and AVA

Screening Assessments	Days -36 to -15 ^a	Notes
Informed consent process	X	
Demographic information	X	
Inclusion/Exclusion criteria	X	
Medical history (includes substance usage and Family history of premature CV disease)	X	
Physical exam including height and weight	X	
Alcohol and Drug Screening	X	
Urinalysis	X	
Vital signs	X	
Hematology and clinical chemistry	X	Refer to Table 4 in CSP [1] for specific laboratory tests.
HIV, Hep B and Hep C screen	X	
Review concomitant medications	X	
Serum or urine pregnancy test	X	
AE/SAE assessment	X	Will capture SAEs reported between Screening visit and Day -1.
Toxin Neutralizing Ab (TNA)	X	
Anti-PA Ab	X	

a. The screening window closes at Day -15 to allow all analyses to be completed to confirm subject eligibility.

Table 2.2 Treatment Group 1: Time and Events for subjects administered AVA

Protocol Activity	Study Visit						Notes
Assessments	Day -1 ^a	Day 1	Day 15 (± 2 days)	Day 29 (± 2 days)	Day 57 (± 2 days)	Day 183 (± 4 days)	
Inpatient visit		↔ X →					
Outpatient visit				↔ X →			
Urinalysis					X		
Admit to unit	X						
Randomization	X						
Discharge from unit		X					The subject will be discharged from the unit after all assessments are completed.
Vital signs	X	X		X	X	X	
Hematology and clinical chemistry	X			X	X		Refer to Table 4 in CSP [1] for specific laboratory tests. On Day 29 the specimen will be collected
Review concomitant medications	X		X	X	X	X	
Serum or urine pregnancy test	X		X	X	X	X	
AVA administration		X	X	X			Each sequential AVA injection will be administered in a different injection site (e.g. alternating arms).
AE/SAE assessment	X	X	X	X	X	X	
Toxin Neutralizing Ab (TNA)		X		X	X	X	On Days 1 and 29 the specimen will be collected prior to AVA injection.
Anti-PA Ab		X		X	X	X	On Days 1 and 29 the specimen will be collected prior to AVA injection.

a. Day -1 is the calendar day preceding Day 1; the designation "Day 0" is not used in this study.

Table 2.3 Treatment Group 2: Time and Events Table for subjects co-administered raxibacumab and AVA

Protocol Activity Assessments	Study Visit								Notes	
	Day -1 ^a		Day 1							

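### As tabulated in both documents, post-dose urinalysis is marked only for the AVA-alone group; the empty Group 2 row should be confirmed against the source table and, if blank there, reconciled

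*Protocol*

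**What the plan says.** **Schedules.** Protocol Section 7.1 and SAP Section 2.6 each give one table per arm.

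- Group 1, AVA alone: "Table 2 Treatment Group 1: Time and Events for subjects administered AVA" and "Table 2.2 Treatment Group 1: Time and Events for subjects administered AVA". Both have a urinalysis row with a single mark, at Day 57.
- Group 2, raxibacumab plus AVA: "Table 3 Treatment Group 2: Time and Events Table for subjects co-administered raxibacumab and AVA" and "Table 2.3 Treatment Group 2: Time and Events Table for subjects co-administered raxibacumab and AVA". Both have a urinalysis row with no mark and no note.

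**Screening.** Protocol Section 7.2 lists urinalysis among the items introduced by "the following data will be collected at the screening visit for all subjects". It does not list urinalysis again in the Day -1 or Day 1 baseline items. Protocol Table 4 places it, as a routine dipstick, under other screening tests.

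**Use of the data.** The secondary safety endpoint in SAP Section 2.2.2 includes "review of vital signs, urinalysis, and clinical laboratory data in the AVA alone and the AVA with raxibacumab treatment groups"; protocol Section 3 has the same content. Protocol Section 7.4 counts urinalysis among the clinical safety observations and refers to Section 7.1 for timing. Protocol Section 9.4.2.3 plans to summarise "changes over time in laboratory parameters, urinalysis and vital signs". SAP Section 4.12.4.4 plans counts and percentages for the non-continuous urinalysis variables.

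**Status of the tables.** Protocol Section 7 makes adherence to the Time and Events Tables a requirement of study conduct. Sections 7 and 7.4 allow safety time points to be changed or added, but on the basis of newly available data.

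**The concern.** The endpoint and both analysis sections treat urinalysis as collected in both arms. As tabulated, only the control arm has a sample after dosing. Because the protocol text defers timing to the tables, a site following them would take a Day 57 urinalysis in Group 1 and none in Group 2.

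At stake is one component of the safety description. A change over time needs a post-dose value, and a side-by-side summary of post-dose results needs values in both arms. If the Group 2 row is truly empty, neither exists for the arm that receives the antibody. The general permission to add time points does not repair this, because it responds to new data and schedules nothing by itself.

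**Working it through.** No sample size, power or error-rate formula bears on this point. The check is a count of marks, row by row, in the two schedules of each document, followed by a search for any text that fills the gap.

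**Step 1. Marks per shared assessment row.** Group 1 counts are the same in protocol Table 2 and SAP Table 2.2.

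| Row | Group 1 | Group 2, protocol Table 3 | Group 2, SAP Table 2.3 |
|---|---|---|---|
| Urinalysis | 1 (Day 57) | 0 | 0 |
| Vital signs | 5 | 5 | 5 |
| Hematology and chemistry | 3 | 3 | 3 |
| Concomitant medications | 5 | 5 | 5 |
| Pregnancy test | 5 | 5 | 5 |
| AVA administration | 3 | 3 | 3 |
| AE/SAE assessment | 6 | 8 | 8 |
| TNA | 4 | 4 | 4 |
| Anti-PA Ab | 4 | 4 | 4 |

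Urinalysis is the only shared assessment row in which Group 2 has fewer marks than Group 1.

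**Step 2. How far the Group 2 grid can be trusted.** Its column positions are not reliable in the extracted text. Read literally:

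- Hematology and chemistry falls on Day -1, Day 15 and Day 29 in the protocol, but on Day -1, 2-6 hours and Day 15 in the SAP, although the row's own note refers to a Day 29 specimen.
- AVA falls at 0 hours, 2-6 hours and Day 15 in the SAP, against the stated Days 1, 15 and 29.
- PK sampling has 8 marks in the protocol and 7 in the SAP; the note lists 7 times (pre-infusion, 30 minutes, 2-6 hours, Days 15, 29, 57 and 183). The discrepancy is 8 - 7 = 1 extra mark in the protocol, not a missing one.

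So marks have mainly moved between columns. Where a count can be checked against Group 1 or against a note, none has fallen short except urinalysis. The two Group 2 grids are displaced differently, yet both show zero for urinalysis.

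**Step 3. Other text.** Protocol Sections 7.2, 7.4 and 9.4.2.3, protocol Table 4, and SAP Sections 2.2.2 and 4.12.4.4 give no post-dose urinalysis visit for Group 2.

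**Step 4. Size if the row is blank.** Scheduled post-dose urinalyses per subject: Group 1 = 1, Group 2 = 0. Under 1:1 allocation the number of Group 2 analyzable subjects depends on where the trial ends:

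- stop at interim 1: 30 / 2 = 15
- stop at interim 2: 100 / 2 = 50
- full enrolment: 534 / 2 = 267

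The scheduled count is 0 of 15, 0 of 50 or 0 of 267. At the protocol's estimated ceiling of 620 randomized, Group 2 would have about 620 / 2 = 310 subjects.

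**The case against.** The strongest reply is that this is one blank cell in a grid plainly damaged by PDF reading, and that such damage is not an error in the plan. Several parts of that reply have weight.

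- Nobody would report the misplaced AVA or hematology marks as plan errors, and the blank should get the same caution.
- The spanning arrows in the inpatient and outpatient rows just above urinalysis appear in the Group 1 tables but not in the Group 2 tables, so content next to this row did differ.
- The AE/SAE row has 8 marks across 9 columns (five other visits plus four Day 1 columns). The text cannot show whether one cell was unmarked by design or a mark was lost.
- A row kept with nothing in it suggests that a sample was intended. That is equally consistent with a mark omitted by the authors and a mark lost in reading.
- The SAP schedule repeats the protocol's rows and notes. Its blank is therefore not independent evidence of what the sponsor intended.

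What stands is that the blank cannot be treated as proven. What does not stand is that it should be ignored. The other shared rows keep at least their Group 1 counts, and a blank carried from the protocol into the SAP explains two zeros more simply than the same mark being lost in two differently displaced grids.

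A reader might also infer that a renal or urinary effect of raxibacumab could not be detected, or that the safety endpoint fails. The documents do not support either inference. Creatinine, BUN and calculated creatinine clearance are in the chemistry panel of protocol Table 4, that panel is scheduled in both groups, and adverse events are collected in both. The safety objective is to describe, and no test on urinalysis is planned.

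**Conclusion.** The inconsistency holds as tabulated. Group 1 has one post-dose urinalysis and Group 2 has none, in both documents, and no other section supplies one. A true blank in the source is the more likely explanation, but this rests on extracted tables with displaced columns and is conditional on checking the source.

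If the blank is confirmed, the raxibacumab arm has screening urinalysis only. The urinalysis component of the secondary safety endpoint, the protocol's summary of change over time and the SAP's counts and percentages would have no scheduled post-dose Group 2 data: 0 of at least 267 subjects at full enrolment, fewer if the trial stops at an interim. Nothing else in the safety endpoint is affected, and the primary analysis is untouched.

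Two stronger statements should be avoided. The documents do not establish that Group 2 was never meant to have the sample; they give no reason for testing only the AVA-alone arm, and the retained row points the other way. Nor do they show that the safety comparison as a whole cannot be made.

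**What to change.** 1. Check the urinalysis row of protocol Table 3 and SAP Table 2.3 against the source tables. If a mark is there, the point is closed.
2. If the row is blank, reconcile both tables with protocol Table 2 and SAP Table 2.2, and with protocol Sections 3, 7.4 and 9.4.2.3 and SAP Sections 2.2.2 and 4.12.4.4, so that both groups have the same post-dose urinalysis. The Group 1 tables mark it at Day 57, which is already a visit for both groups.

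The cost is a correction to one table in each document and one dipstick per Group 2 subject at a scheduled visit: 267 at the target enrolment, or about 310 if 620 are randomized. No change to sample size, analysis method or visit structure is needed.
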